If evaluation of the clinical indicators suggest the presence of significant bacterial infection of the wound, swab culture, utilizing swab technique [126] will be performed to confirm or reject the presence of significant bacterial infection severe enough to warrant the subject terminated from the study. The swab culture will be performed using a laboratory-provided swab that is pressed down over a 1 cm² area of the wound that is then delivered to the lab for analysis to determine Colony-Forming Units (CFUs) per gram of viable wound tissue and beta-hemolytic Streptococcus per gram of tissue. The findings of a positive or negative swab culture utilizing Levine's technique will be interpreted according to the following criteria:

- Positive culture indicating presence of bacterial infection: $\geq 1,000,000$ Colony-Forming Units (CFUs) per gram of viable wound tissue OR containing beta-hemolytic Streptococcus per gram of tissue at any level.
- Negative culture indicating absence of bacterial infection: $< 1,000,000$ Colony-Forming Units (CFUs) per gram of viable wound tissue OR no beta-hemolytic Streptococcus per gram of tissue at any level.

Tissue specimens will be obtained from the chronic wounds using 1) wound exudate, 2) broad Z-technique, and 3) Levine technique [126]. Acquisition of swab specimens was followed with a wound tissue biopsy. The diagnostic validity of each technique was determined by associating the quantitative culture findings of each swab specimen with the culture findings of concurrent tissue specimen (gold standard). Levine's technique performed best of the three swab techniques in terms of all four validity parameters: sensitivity was, specificity, positive predictive value, and accuracy.

Bio-burden

Bio-burden will be assessed using qPCR to quantify bacterial load from serial tissue specimens. Specific organisms that will be quantified using qPCR are listed in the table below. Bone, soft tissue will be sent to Research and Testing Laboratory (Lubbock, TX) for analysis.

Specific organisms (and two resistance factors) to be quantified using qPCR.			
E. faecalis	E. faecium	S. epidermidis	M. morgani
K. pneumonia	S. aureus	C. striatum	S. haemolyticus
S. agalactiae	S. marcescens	F. magna	S. mutans
S. pyogenes	H. influenzae	P. mirabilis	Vancomycin res.
C. albicans	M. catarrhalis	C. parapsilosis	Methicillin res.
P. aeruginosa	S. pneumoniae	A. baumannii	Total Bioburden

Osteomyelitis

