Osteomyelitis will be diagnosed when radiographic and clinical signs are consistent with bone infection. This diagnosis will be confirmed with imaging, bone biopsy, culture or histopathology as most applicable to the individual subject. The bacterial pathogens and sensitivities from bone and soft tissue cultures will be recorded and direct antibiotic therapy applied, if necessary [79].

Study Procedures

Procedures and Evaluations During the Research

The time period from Day 0 to up to 12 weeks will encompass the study therapy administration and evaluation phase. The precise therapy employed will be determined according to subject randomized group allocation, and the duration of the study therapy administration phase will be determined according to individual subject wound healing and status progression and safety evaluations. The study therapy administration phase will comprise the

following progressive activities, as applicable, and will be initiated in the inpatient clinic setting: therapy administration, , and weekly or standard of care wound healing and safety evaluation. The study therapies are delivered in continuous mode throughout the individual subject's entire study therapy administration phase; with the only consistent interruption being for the three times a week wound dressing changes. There will likely be other minimal daily interruptions such as to allow for subject showering and bathing. Therapy administration phase will continue until study wound is ready for closure by secondary intention, after which time the therapy will be discontinued.

Therapy Administration

- Therapy phase to be continued until wound is ready for closure by secondary intention
 - During this therapy administration phase, all subjects will receive NPWT therapy for 4 weeks or until the wound is deemed ready for surgical closure, whichever occurs first. This time point will serve as the individual subject's study evaluation endpoint.
 - Study wound readiness for surgical closure in this study is defined as the time point (evaluation visit) at which the following three factors pertaining to the status of the study wound are determined to co-exist by the study investigator:
 - deep structures (bone, tendon, joint) are covered with granulation tissue
 - the wound depth is < 2 mm
 - the wound bed is ready for skin graft, delayed primary closure or rotational flap to cover the defect.

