 - The subject will re-enter the therapy administration phase including the weekly or standard of care efficacy and safety evaluation test site visits and procedures.

Home Health Visits

The study therapy will only be given while the subject is in the hospital. If the subject's wound is not ready for closure during the hospital stay, the subject will continue NPWT at home. NPWT at home will be without irrigation. If the subject continues to receive NPWT after hospital discharge, the subject will be seen twice weekly by a home health nurse for dressing changes. The home health nurse will collect sitting blood pressure and pulse rate. Amount, type and character of wound drainage will be documented, as well as any adverse events and changes to concomitant medications. Offloading will be reapplied after dressing changes. At the same time, subject will continue to be followed by the study doctor during regular post-operative visits at outpatient clinic. If the wound closes, End of study visit will be performed and she/he will see the study doctor at outpatient clinic to have the closed wound checked.

Safety and Efficacy Evaluation

During the study therapy administration and evaluation phase, the subject will attend once weekly or standard of care test site visits, commencing at the end of Week 1 of therapy administration and ending at the weekly or standard of care visit where the wound is determined ready for surgical closure and the therapy administration process is complete.

- Weekly or standard of care Efficacy Evaluations
 - Digital Photography of the Study Wound
 - Wound Measurement (using a ruler and the eKare Insight System)
 - Granulation Tissue Estimation
 - Additionally, at the final week of efficacy evaluation test site evaluation, Subject Satisfaction with Study Procedure Outcome Evaluation will be performed.
- Weekly or standard of care Safety Evaluations
 - Safety Measures
 - Debridement Indication
 - Degree of Pain Rating
 - Infection Evaluation: encompassing swab culture and osteomyelitis assessment, if indicated.
- Inpatient Tissue Samples
 - Tissue samples will be taken and kept, for research, at inpatient study visits prior to wound closure for the following analyses.
 - For bacterial analyses
 - For gene expression analyses
 - After wound closure, no samples will be taken unless wound reoccurrence occurs.
 - Samples will be approximately 0.25-0.5 cm³ in size

- Bio-burden: qPCR evaluation
- Other Activities

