Wound Assessment/ Debridement	X	X	X		X		
Tissue /bone ¹ / wound culture samples for qPCR cultures & bioburden analysis		X	X (Subsequent surgery)				

			while Inpatient)				
NPWT/NWPT (i) randomization/dressing application/changes		X	X	X (Weeks 2-4)	X (Weeks 2-4)		NWPT for maximum 4 weeks after baseline(Day0 surgery) if wound is not closed in the hospital
SF-36 Questionnaire	X					X	
Hyperspectral Imaging Analysis	X						To occur prior to surgery
Discharge Instructions			X		X		
Offloading			X	X	X		At hospital discharge & continuing to Week 12
Adverse Events		X	X	X	X	X	
Current/concomitant antibiotics	X	X	X	X	X	X	
Wound imaging/measurement		X	X		X	X	While active study wound is present
Neuropathy Disability Score in Patients with Diabetes	X						

¹ Only if performed as a necessary part of standard of care.

² Subjects who heal before week 12 will exit the study and complete EOS visit.

Biostatistics

Sample Size Justification:

There are no published data with the Cardinal PRO negative pressure wound therapy (NPWT) device with or without irrigation in order to determine an estimate of the sample size for this study. One of the purposes of this project is to obtain data, so we can power a larger multicenter study. Even though the KCI NPWT device with irrigation has been commercially available, there is little data about volume change or wound healing in the population we are studying.

The previous sample size justification was based on a comparison of the proportion of wounds expected to achieve surgical closure. The proportion of subjects with closed wound was 62% using traditional KCI NPWT and 94% using NPWT with periodic irrigations with Prontosan. For the sample size, we estimated 85-90% wound closure with NPWT with irrigation and 60% wound closure with NPWT without irrigation. We assume the NPWT devices (KCI and Cardinal) without irrigation would have similar results.

Equations

The following formula was used to estimate the required sample size, n , for the relative difference in proportions P_1 and P_2 .

$$n = \frac{\left(Z_{\alpha/2} \sqrt{2P(1-P)} + Z_{\beta} \sqrt{P_1(1-P_1) + P_2(1-P_2)} \right)^2}{(P_1 - P_2)^2}$$

where

$$P = \frac{P_1 + P_2}{2}$$

Using the formula above and assuming 90% wound closure with NPWT with irrigation and 60% wound closure with NPWT without irrigation and a type I error of 0.1, the required sample size is about 25. If a Type I error of 0.05 is assumed, then the required sample size is about 31.

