The inpatient stay and post-operative visits are covered under a 90-day global payment which is inclusive of all procedures, devices, testing and ancillaries associated with the surgical procedure, including NPWT. Subjects’ insurance will not be charged any additional amount for the NPWT devices used in the study. The KCI devices are standard at Parkland; Cardinal is providing their devices. But again, in neither situation would a subject or their third party pay or be charged anything additional.

Survival Analyses Models

The primary analytical method presented in this report is based on a time-to-event strategy using Kaplan-Meier estimates, followed by a log-rank test. This statistical procedure provides a comparison of the distribution of events between the 2 treatment groups. In addition to the event rates calculated for the post-baseline time points, the median time to 100% closure, 75% closure, and 76-100% wound bed granulation will also be calculated. This same methodology will also be used to compare the overall duration of treatment, and within the individual patient subsets defined by their outcome status.

A Cox proportional hazard model will be used to relate time to specific events to various risk factors. The main modeling strategies will look at the time to adverse events with time being measured from the time of surgery or the time of NPWT application until either an adverse event occurs, the patient is considered healed, or the end of the study. Cox proportional hazard model allows the independent variables to be continuous covariates or categorical or binary factors. The type of NPWT treatment will be the main independent variable. We will use multivariate proportional hazard regression analysis methods to investigate what factors are significant for non-healing patients or patients that have complications. Similar to the logistic regression, maximum likelihood estimates of model parameters along with tail probabilities (p-values) and confidence intervals for parameters

will be derived based on asymptotic inferences. For the proportional hazard model the ratio of the hazards for two subjects one with and one without diabetes, given that the subjects have the same values for other parameters can be estimated from the model coefficients. Repeated measures ANOVA and ANOVA will be used to evaluate changes in quantitative cultures and laser Doppler measurements over time and between treatment groups.

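### Log-rank tests of treatment duration within outcome-defined subsets are not randomised comparisons, and overall duration can be read as resource use but not as benefit

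*Combined protocol and SAP*

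**What the plan says.** The Survival Analyses Models section describes a primary analytical method "based on a time-to-event strategy using Kaplan-Meier estimates, followed by a log-rank test". It then adds that the same approach will serve to "compare the overall duration of treatment, and within the individual patient subsets defined by their outcome status". It does not define outcome status, and it does not say which ends of treatment are events and which are censored.

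Therapy can end in several ways:

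- **Readiness or time limit.** Therapy Administration states that "all subjects will receive NPWT therapy for 4 weeks or until the wound is deemed ready for surgical closure, whichever occurs first". A note in the Schedule of Events repeats the limit: "NWPT for maximum 4 weeks after baseline(Day0".
- **Infection.** The Swab Culture section provides for a culture to confirm or reject the "presence of significant bacterial infection severe enough to warrant the subject terminated from the study".

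Other text does not fit a single four-week course. Procedures and Evaluations During the Research says: "The time period from Day 0 to up to 12 weeks will encompass the study therapy administration and evaluation phase". Therapy Administration also has therapy continuing until the wound is ready to close by secondary intention. If a closed wound re-opens or shows infection, Therapy Administration and Post Procedure Administration Activities have NPWT reapplied, and "The subject will re-enter the therapy administration phase". Home Health Visits confines the study therapy to the hospital stay but continues NPWT at home without irrigation.

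Sample Size Justification assumes 85-90% closure with irrigation and 60% without, and similar results for the two devices without irrigation. Objective 2 (H2) expects fewer infections with irrigation.

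**The concern.** A subset defined by outcome is chosen by the result that treatment is meant to change. If irrigation closes wounds that would otherwise stay open, its closed subset contains those harder wounds and the control arm's does not. A log-rank test between the two then compares different kinds of wound. The arm that closes more wounds can look slower for that reason alone.

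Overall duration has a different difficulty, one of interpretation. A short course may mean early readiness or early failure, and the curve alone does not separate them. The study states an economic aim, so treatment duration is likely to be read directly by clinicians and payers.

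**Working it through.** **The plan's own figures.** The plan gives no design figure for duration. Its closure rates come from the sample-size formula, with P1 = 0.60, P2 = 0.90 and P = 0.75. At type I error 0.10: (1.645 × √0.375 + 0.842 × √0.33)² / 0.30² = 24.69, against about 25 stated. At 0.05 the result is 31.50, against about 31 stated. The closure assumptions are therefore read correctly. Enrolment of 90 at 1:1:1 gives 30 per arm.

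**Closed-wound subset (timings assumed).** In both arms, 60% of subjects have wounds that become ready uniformly between days 14 and 24 (mean 19). Irrigation leaves those unchanged and makes an extra 30% ready uniformly between days 22 and 28 (mean 25). All other subjects stay on therapy to day 28.

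- Mean among closed wounds, control: 19.0 days.
- Mean among closed wounds, irrigation: (0.6 × 19 + 0.3 × 25) / 0.9 = 21.0 days.
- At 85% closure: (0.6 × 19 + 0.25 × 25) / 0.85 = 20.8 days.
- Mean over all subjects, control: 0.6 × 19 + 0.4 × 28 = 22.6 days.
- Mean over all subjects, irrigation at 90% closure: 0.6 × 19 + 0.3 × 25 + 0.1 × 28 = 21.7 days.

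In 3,000 simulated trials of this case with 30 per arm (about 18 and 27 closed wounds), the closed-subset log-rank found irrigation significantly slower in 68% and faster in none. Irrigation could also shorten the ordinary wounds' time by about 16% and still show no gain in this subset mean: 0.6 × s × 19 + 7.5 = 0.9 × 19 gives s = 0.842. If the extra wounds closed at the same mean of 19 days, the means would not differ. The direction therefore depends on the extra wounds being slow.

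**Overall duration (infection-stop rates assumed; the documents give none).** The readiness hazard is the same in both arms, λ = −ln(0.4)/28 per day. The infection-stop hazard is h = −ln(1−q)/28, where q is the net probability by day 28. Every stop is counted as an end of treatment. Median duration = ln 2/(λ+h). Hazard ratio for all stops = (λ+h₂)/(λ+h₁). Cumulative incidence of readiness by day 28 = λ/(λ+h) × [1 − 0.4(1−q)]. Rejection rates come from 3,000 simulated trials with 30 per arm, two-sided 5%.

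| Infection stops q | Median days | Hazard ratio | Log-rank rejects | Readiness by day 28 |
|---|---|---|---|---|
| 10% vs 10% | 19.0 vs 19.0 | 1.00 | 5.2% | 57.4% vs 57.4% |
| 5% vs 15% | 20.1 vs 18.0 | 1.11 | 6.6% | 58.7% vs 56.1% |
| 5% vs 25% | 20.1 vs 16.1 | 1.24 | 10.5% | 58.7% vs 53.3% |
| 5% vs 40% | 20.1 vs 13.6 | 1.47 | 22.5% | 58.7% vs 48.8% |

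In the last two rows nearly all rejections (10.0 of 10.5 points and 22.4 of 22.5) show the arm with more infection as shorter. The durations truly differ in rows two to four, so these are detections of a real difference and not false positives. The cumulative incidence of readiness points the other way and shows that arm as worse. A log-rank on readiness alone, with other stops censored, rejects in 5.0-5.5% of trials, as it should when readiness hazards are equal.

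**The case against.** The strongest defence concerns overall duration. Compared by arm in everyone randomised, it is a randomised comparison, and total NPWT time whatever the stop reason is a legitimate resource quantity given the economic aim. Treatment duration is not a listed primary or secondary endpoint, and nothing says that shorter will be read as better. Excess failures would also show elsewhere: infection incidence is a secondary endpoint, time to adverse events is modelled, and withdrawals for adverse events are distinguished on the CRF. All of this stands, and it confines the overall-duration concern to interpretation.

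A reader might infer more than the documents support:

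- **That the overall test has an inflated error rate.** It does not. With equal stop rates it rejects in 5.2% of trials; otherwise it detects a true difference in duration.
- **That the plan scores infection stops as events.** It sets no rule. Such a subject leaves the study, and an analyst could censor there. That would be unbiased for readiness only if infection were unrelated to healing, whereas the plan's Background links infection with delayed healing.
- **That the four-week limit biases the log-rank.** A limit falling on the same day for everyone adds nothing. In the 5% vs 25% case, rejection was 10.5% with the limit as an event and 11.3% with it censored, within simulation error.
- **That every never-ready subject has a four-week duration unless they fail or leave.** The text reaching to 12 weeks and the re-entry rule make this insecure.

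The closed-subset example was built to show a mechanism and predicts nothing. The objection to outcome subsets does not depend on it.

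**Conclusion.** The concern holds for the outcome-defined subsets. The tests condition on a post-randomisation result that the plan expects to differ for the irrigation contrast. For PRO against KCI without irrigation the plan assumes similar closure, so less distortion is expected there, but the tests would still not be randomised comparisons. The illustrated size is an apparent disadvantage of about 2 days (21.0 against 19.0) for the arm that closes more wounds. It rests on assumed timings and on the extra wounds being slow. Because outcome status is undefined, the number of such tests cannot be counted.

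Overall duration is valid as a resource measure and not as evidence of benefit. If infection stops count as ends of treatment, an arm with more of them has a shorter duration: about 2 days in the median at 5% vs 15%, and about 4 days at 5% vs 25%, both under assumed rates. Neither duration nor administrative censoring can be defined until the therapy passages agree. This is a supplementary analysis and the primary endpoint is wound-volume reduction, so the importance is moderate.

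**What to change.** 1. Remove the between-arm log-rank tests within outcome subsets. Define outcome status and report durations by outcome and arm descriptively, without p-values.
2. Keep total treatment duration in all randomised subjects as a resource measure. State which ends of therapy count and whether home NPWT and re-entry periods are included, and tabulate stop reasons by arm.
3. Base any efficacy reading on time to readiness for closure, with stops for infection or other failure as competing events, reported as cumulative incidence by randomised arm.
4. Reconcile Procedures and Evaluations During the Research, Therapy Administration, Home Health Visits, Post Procedure Administration Activities and the Schedule of Events on when therapy ends and restarts. Then define administrative censoring from the reconciled text.

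The cost is analysis-plan wording, the reconciliation of those passages and one stop-reason field on the CRF, which already separates adverse-event withdrawals. The p-values given up could not have been interpreted as treatment effects.

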- Comparison of the following variables between the groups: granulation tissue integrity including hypergranulation state, time to close, flap/graft take, dehiscence, and reoccurrence.

Objective 2

To compare bacterial load, quantitative cultures, and clinical infections in wounds treated with NPWT PRO compared to wounds treated with NPWT PRO with simultaneous irrigation.

H1: Bacterial load measured with quantitative polymerase chain reaction (qPCR) will be progressively lower with continuous irrigation.

H2: Patients treated with simultaneous irrigation and NPWT PRO will have fewer infections defined by qPCR and clinical criteria.

Primary Endpoint:

- Comparison of reduction in bacterial load in wounds treated with NPWT and NPWT with simultaneous irrigation.

Secondary Endpoints:

- Comparison of incidence of infection in wounds treated with NPWT and NPWT with simultaneous irrigation.
- Infection-induced necrosis
- Infection reoccurrence post-closure

Objective 3

Assess changes in molecular markers associated with wound healing and regeneration of healthy tissue.

H1: NPWT PRO with simultaneous Irrigation will improve the levels of growth factors, cytokines, and other molecular markers over NPWT PRO alone.

H2: Negative pressure wound therapy will drive molecular changes in growth factors and other cytokines associated with regeneration of healthy tissue.

Primary Endpoint:

- To compare changes in genes and other molecular markers associated with wound healing between wounds treated with NPWT and NPWT with simultaneous irrigation.

Secondary Endpoint:

- To compare the addition of simultaneous irrigation on gene expression and expression of molecular markers from baseline.

Objective 4

Quality of Life and Patient Satisfaction Analyses

H1: Patients treated with the NPWT PRO device will show greater patient satisfaction with treatment than those treated with KCI Ultra NPWT therapy.

Primary Endpoints:

- To compare Quality of Life and Patient Satisfaction between patients treated with NPWT PRO versus patients treated with KCI Ultra NPWT therapy.
- To compare Quality of Life and Patient Satisfaction between patients with wounds treated with NPWT PRO versus NPWT PRO + SI.
- Evaluate functional status, using the Short Form 36 (SF36). These will be administered at baseline and at the last study visit.

Subjects and Recruitment

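### Repeated-measures ANOVA does not fit bacterial-load samples whose number and timing depend on the wound's course, and the plan's two sampling rules conflict

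*Combined protocol and SAP*

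**What the plan says.** The primary endpoint of Objective 2 is: "Comparison of reduction in bacterial load in wounds treated with NPWT and NPWT with simultaneous irrigation". The Bio-burden paragraph under Infection Evaluation gives the measurement: "Bio-burden will be assessed using qPCR to quantify bacterial load from serial tissue specimens". The only method given for change over time is in Biostatistics, Survival Analyses Models: "Repeated measures ANOVA and ANOVA will be used to evaluate changes in quantitative cultures", and the same sentence extends this to laser Doppler readings, with comparisons across time and between arms. The Schedule of Events describes the specimens as "wound culture samples for qPCR cultures & bioburden analysis", and this wording is what ties the ANOVA sentence to the qPCR load.

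Two places say when specimens are taken:

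- **Schedule of Events.** Day 0, and then, in the Week 1 inpatient column (which may run into Week 2), an entry that begins "X (Subsequent surgery" and is limited to subjects still in hospital. The home-health, clinic and end-of-study columns are empty for this row.
- **Safety and Efficacy Evaluation, Inpatient Tissue Samples.** "Tissue samples will be taken and kept, for research, at inpatient study visits prior to wound closure for the following analyses". No further operation is required. Sampling stops at closure unless the wound recurs.

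The Standard of Care Regimen makes a repeat debridement depend on the state of the wound. For bacterial load, Biostatistics states no sampling day, number of occasions, measurement scale or missing-data rule. The Microbial Diversity subsection covers bacterial composition and does not test total load.

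**The concern.** Classical repeated-measures ANOVA assumes that every subject is measured on the same set of occasions, and subjects with a gap drop out of it. This design supplies no such set. Under the schedule, a follow-up sample exists only if the wound needed another operation in hospital. Under the body text, samples continue until closure or discharge, and those dates also follow the wound. Either way, who remains in the analysis can depend on the outcome.

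At stake is the primary comparison of Objective 2. Its first hypothesis expects load to keep falling under irrigation, and the Innovation section asks how long eradication takes, so the later and sparser samples matter. The scale is also left open, although the plan's own background relates healing to the logarithm of the bacterial count.

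**Working it through.** **1. The plan's own figure.** The only sample-size calculation is for surgical closure, 60% vs 90%, power 0.80. With P = 0.75, n = (z√(2·0.75·0.25) + 0.842√(0.24 + 0.09))² / 0.30².
- Two-sided alpha 0.10: (1.645·0.6124 + 0.842·0.5745)² / 0.09 = 24.69 (stated 25).
- Two-sided alpha 0.05: (1.960·0.6124 + 0.842·0.5745)² / 0.09 = 31.50 (stated 31).

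The figures reproduce to within one patient, but they concern closure. The plan gives no figure for bacterial load.

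**2. How many subjects would have follow-up operations.** Inputs: the preliminary-data table under Sample Size Justification gives surgeries of 3.0 ± 0.9 (NPWT alone), 2.4 ± 0.9 (6-minute dwell) and 2.6 ± 0.9 (20-minute dwell). Ninety subjects randomised 1:1:1 give 30 per arm. Assumption: the counts include the first operation, so one follow-up means at least 2 surgeries and two follow-ups mean at least 3.

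Formula: P(surgeries ≥ k) = 1 − Φ((k − 0.5 − mean)/0.9).

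| | NPWT alone | 6-minute | 20-minute |
|---|---|---|---|
| At least one follow-up (k = 2) | Φ(1.667) = 0.952 | Φ(1.000) = 0.841 | Φ(1.222) = 0.889 |
| of 30 | 28.6 | 25.2 | 26.7 |
| At least two follow-ups (k = 3) | Φ(0.556) = 0.711 | Φ(−0.111) = 0.456 | Φ(0.111) = 0.544 |
| of 30 | 21.3 | 13.7 | 16.3 |

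A wider distribution, 1 + Poisson(mean − 1), gives 86% vs 75–80% for at least one and 59% vs 41–48% for at least two. If the counts exclude the first operation, the rows shift by one, and at least two follow-ups becomes 95% vs 84–89%.

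**3. What a complete-occasion analysis would discard.** Suppose the occasions are Day 0 plus two follow-ups, under the schedule's rule. Of 60 subjects in the two PRO arms, 60 − (21.3 + 13.7) = 25.0 would drop out with the 6-minute rates, and 60 − (21.3 + 16.3) = 22.4 with the 20-minute rates. Of these, (28.6 − 21.3) + (25.2 − 13.7) = 18.8 and (28.6 − 21.3) + (26.7 − 16.3) = 17.7 would have a follow-up sample that goes unused.

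**4. Size of a selection effect with no true difference.** Let the follow-up load have SD 1 and correlation ρ with the propensity to be sampled, higher load making sampling more likely. If a proportion p is sampled, the mean load among those sampled is ρ·φ(c)/p, with c = Φ⁻¹(1 − p).
- First follow-up, p = 0.952 vs 0.841: ρ(0.2881 − 0.1048) = 0.183ρ. At ρ = 0.7 this is 0.13 SD against irrigation.
- Second follow-up, p = 0.711 vs 0.456: ρ(0.8695 − 0.4806) = 0.389ρ. At ρ = 0.7 this is 0.27 SD.
- With the 20-minute rates: ρ(0.2129 − 0.1048) = 0.108ρ and ρ(0.7289 − 0.4806) = 0.248ρ, or 0.08 and 0.17 SD at ρ = 0.7.

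The range ρ = 0 to 0.7 is an assumption; the documents give no value. At ρ = 0 there is no shift.

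**5. What a mixed model can and cannot repair.** These are illustrative simulations with an assumed true contrast of −1.0 log10; the variances and the strength of the dependence are also assumed.
- Sampling driven by the previous load (30 per arm): complete cases gave −0.91 to −0.99, and a likelihood-based analysis about −1.0.
- Sampling driven by the current load: complete cases gave −0.77 to −0.98, and the likelihood-based analysis −0.76 to −0.98, which is no material gain.

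**The case against.** Several counter-arguments have force.

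- **Sampling is not clearly limited to re-operation.** A reader of the schedule might infer that only re-operated subjects yield follow-up samples. The Inpatient Tissue Samples text does not say so, and therapy starts in hospital for everyone. This stands: re-operation-only sampling is one of two conflicting readings. Under the other, most subjects could be sampled, but at unequal numbers and times.
- **The endpoint link is not explicit.** Objective 2 names bacterial load and quantitative cultures separately, and the ANOVA sentence covers the latter. If the link is wrong, the plan has no stated test for change in total load, and the same remedy is needed.
- **The direction is not settled.** It is tempting to say that the fastest-clearing wounds are the ones lost. However, surgical closure takes place in the operating room, so a wound closed early in hospital may be sampled then. Subjects without a later sample may include those discharged unclosed to home NPWT. In the preliminary table 94% of wounds closed in the 6-minute group against 62% with NPWT alone.
- **The arm difference is projected.** The cohort was retrospective and used PHMB with dwell times; this trial uses continuous saline.
- **Deletion is inferred.** The plan does not say that incomplete subjects are dropped, and a two-point analysis would fit its wording. That leaves the number of occasions and the missing-data rule undefined, which is part of the point.

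**Conclusion.** The point holds in a limited form. Under either sampling rule the follow-up samples have no common schedule, so classical repeated-measures ANOVA is a poor fit for this endpoint and would drop subjects and waste samples. On the preliminary cohort's figures the loss is small if one follow-up is needed (about 5% vs 11–16%) and substantial if two are needed (about 29% vs 46–54%). These percentages rest on a normal approximation, on counts that include the first operation, on the schedule's rule, and on carry-over from PHMB instillation to saline.

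The bias is probably modest and its sign is not certain. Step 4 runs against irrigation only because it assumes that higher load brings more sampling. A difference between arms remains a projection. Nor should a reader infer that a mixed model restores the full contrast: it does so only where earlier observed loads explain the sampling, whereas the plan ties debridement to the wound's condition when it is examined.

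**What to change.** - Reconcile the Schedule of Events with the Inpatient Tissue Samples text on when samples are taken, since this decides which data exist.
- State that the analysis concerns qPCR total load, on the log10 scale.
- Replace repeated-measures ANOVA for this endpoint with a linear mixed model that uses all samples at their actual day. Include arm, time and arm-by-time terms. Treat the baseline value as one of the modelled outcomes, so that subjects with only a baseline sample are retained. Report the arm contrast at one stated day, chosen early enough that both arms still contribute samples.
- Add a sensitivity analysis in which the chance of being sampled depends on the current load, over a stated range.
- Report by arm the number and timing of samples and the reason sampling ended.

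The cost is SAP wording and a little more analysis work; the change of model needs no new samples. The model relies on data being missing at random, which may fail here but is a weaker assumption than complete-case analysis makes. These choices should be fixed before any results by arm are seen.
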